#### 4.2.1. Screening

Within 30 days of the screening visit (defined as day of consent signing), subjects who are eligible will enter the treatment period and start treatment (or dosing) on Day 1.

#### **4.2.2. Treatment Period**

Subjects will be randomly assigned to either GSK2982772 60 mg or placebo orally three times daily (approximately 8 hours apart) for 84 days (12 weeks). Subjects that were randomised prior to protocol amendment 03 being approved in each country were randomly assigned to either GSK2982772 60 mg or placebo orally two times daily (approximately 12 hours apart) for 84 days (12 weeks).

Further guidance and information for study treatment and dosing are provided in the Study Reference Manual (SRM).

During the 84 day (12 week) treatment period, subjects will attend the clinical site for visits on Days 1, 8, 15, 29, 43, 57, 71 and 85. At specific visits, subjects must not take study treatment prior to their scheduled visit (see Section 7.1). On Days 22, 36, 50, 64 and 78, each subject will be contacted by telephone and asked about their general health, study medication compliance and diary card completion. Subjects will be given a diary card at each of the visits on which they will be instructed to record their daily study medication and concomitant medication taken and any adverse events.

#### **4.2.3. Follow-up Period**

After the Treatment Period, the subject will enter the Follow-up Period which lasts for 28 days post the last administration of study medication, in order to complete follow-up assessments per the Time and Events Table (see Section 7.1).

### **4.3. Type and Number of Subjects**

A sufficient number of subjects will be screened so that approximately 24 subjects with moderate to severe RA are randomised into the study on a TID regimen. Prior to protocol amendment 3 being approved in each country, no more than 18 subjects will be randomised into the study on a BID regimen. Should the overall drop-out rate be higher than anticipated, additional or replacement subjects may be randomised (up to an overall maximum of 48) into the study at the discretion of the Sponsor.

### **4.4. Design Justification**

As this is the first trial of GSK2982772 in subjects with RA, the primary endpoint is the safety and tolerability of GSK2982772. In addition, this study will include assessments of target engagement and downstream PD effects of GSK2982772, to understand whether GSK2982772 is inhibiting the pathway of interest in this disease.

The 12 week duration of treatment is based on review of previous proof of mechanism and proof of concept studies in RA and is limited by the supporting 13 week toxicology studies. It is expected that an effective therapy should cause group level changes in the mechanistic parameters by the 12 week time point.

The subjects will be randomised in a 2:1 ratio to GSK2982772 60 mg three times daily (TID) and placebo respectively. The primary objective of this study is to assess safety and tolerability, and assessment of this is most valuable in a placebo controlled study.

The placebo group was also deemed necessary as autoimmune diseases naturally fluctuate in severity. However, the size of the placebo group has been kept to a minimum. All subjects will be allowed to continue standard of care therapy including non-biologic DMARDs during the study, provided that the medication and dose is stable throughout the study.

#### 4.5. Dose Justification

The initial selection of the 60 mg BID dose being tested in this study is based on the safety, PK, and PD data from the First Time in Human (FTiH) study, 200975. GSK2982772 administered at 60 mg BID for 14 days was well tolerated and no safety concerns were identified. A BID dosing regimen was initially selected over a QD dosing regimen due to the short half-life of GSK2982772 in humans (~2h). Based on preliminary PK/PD modelling of ex-vivo RIP1 target engagement and GSK2982772 concentrations from the multiple dose ascending part of Study 200975, a 60 mg BID dose was predicted to have on average 95% RIP1 target engagement in blood and approximately 90% of subjects will have >90% target engagement in blood at  $C_{min}$  using a novel in-house ex-vivo PD/target engagement assay based solely on the TNF pathway which is believed to be a key component of the RIP1 pathway.

However, based on final PK/PD modelling from the full repeat dose part of the Study 200975 (up to 120 mg BID), a 60 mg BID dose is now predicted to have on average 99% RIP1 target engagement in blood and approximately 90% of subjects will have >85% target engagement at  $C_{min}$ . This is lower than our target of achieving >90% target engagement in at least 90% of subjects at  $C_{min}$ . Therefore, a 60 mg TID cohort is now being proposed.

The  $C_{min}$  values at 60 mg TID are predicted to be approximately 3.5 fold higher than for 60 mg BID. Using the final PK/PD, a 60 mg TID dose is predicted to have on average 99% RIP1 target engagement in blood and approximately 90% of subjects will have >96% target engagement at  $C_{min}$ . No data are currently available about the distribution of GSK2892772 into the synovium. Based on data in non-steroidal anti-inflammatory drugs (NSAIDs), the synovial fluid concentrations fluctuate to a much lesser extent than those in plasma [Netter, 1989]. Peak drug concentrations are generally lower in synovial fluid but are similar to plasma at later time points. Assuming the same is true for GSK2982772, a 60 mg TID dose should provide similar RIP1 target engagement at the site of action as predicted in blood.

#### **4.6. Benefit:Risk Assessment**

Summaries of findings from both clinical and non-clinical studies conducted with GSK2982772 can be found in the IB [GlaxoSmithKline Document Number [2014N204126\\_02](#)]. The following section outlines the risk assessment and mitigation strategy for this protocol:

## 4.6.1. Risk Assessment

Potential Risk of Clinical Significance	Summary of Data/Rationale for Risk	Mitigation Strategy
Investigational Product (IP) GSK2982772		
Central Nervous System (CNS) effects	
Non-clinical data: In the 4-week GLP toxicology study, CNS findings were observed in 4/12 monkeys which were administered 100 or 300 mg/kg/day. CNS findings included uncoordination, irregular gait, trembling, hunched appearance, and decreased activity. The clinical relevance of these findings in humans is not known. The NOAEL for this study was determined at 10 mg/kg/day.
 
In the 13-week GLP toxicology study, there were no CNS findings observed in monkeys administered 10, 30 or 100 mg/kg/day. The NOAEL for this study was determined at 30 mg/kg/day.
 
Clinical data: A First Time in Human (FTiH) study with single ascending and multiple ascending dose study has been performed in 67 healthy male volunteers to date. See Investigator's Brochure (IB) [GlaxoSmithKline Document Number 2014N204126_02]. No drug-associated CNS adverse events were identified and no Serious Adverse Effects (SAEs) were reported.
	
Subject Selection:
 
 
Subjects with known history of significant neurologic disorders including but not limited to progressive multiple sclerosis (MS), Amyotrophic lateral sclerosis (ALS), Alzheimer's and dementia will be excluded.
 
Individuals with potentially increased susceptibility for neurologic effects will be excluded based on medical history at screening.
 
 
Subject Monitoring:
 
 
Subjects will be monitored for standard CNS-related adverse events.
 

Immunosuppression	The possibility of immunosuppression, including an increase in the frequency and/or severity of infection, may result from the intended pharmacologic effect of GSK2982772. This may be enhanced in subjects taking other immunomodulating drugs or corticosteroids.	
Subject Selection:
 
 
Subjects with recurrent, chronic or active infections will be excluded from the study.
 
Subjects will be screened for TB, HIV, Hepatitis B and
 

Potential Risk of Clinical Significance	Summary of Data/Rationale for Risk	Mitigation Strategy
	
Clinical data: In the FTiH study, no SAEs were reported. One subject experienced an Adverse Effect (AE) herpes zoster approximately 27 days after receiving his last dose with GSK2982772 or placebo. The blinded Investigator determined this to be potentially drug-related.
	
C, and excluded from the study if positive.
 
Subject Monitoring:
 
 
Subjects will be monitored for signs of infection.
 
See Individual Stopping Criteria for atypical or opportunistic infections (Section 5.4.1).
 

Vaccinations	
There is a theoretical risk that GSK2982772 could decrease an individual's immune response to vaccines or allow symptoms to develop following vaccination with a live vaccine when administered while on therapy.
	
Subject Selection:
 
 
Attenuated or live vaccines should not be administered to subjects from 30 days prior to the first dose of GSK2982772, during the study and for 5 half-lives plus 30 days (total 32 days) after GSK2982772 is discontinued.
 
If indicated, non-live vaccines (e.g. inactivated influenza vaccines) may be administered while receiving GSK2982772 based on a treating physician assessment of the benefit:risk (e.g., risk of theoretical decreased responsiveness).
 
Investigators will be expected to have followed local and/or national guidelines with respect to vaccinations, including against influenza and pneumococcus, in subjects with RA.
 

Respiratory	
Non-clinical data: In the single dose Safety Cardiovascular (CV) and Respiratory Study in monkeys, a decrease in minute volume (MV) and respiratory rate was observed at all doses (10, 100, and 300 mg/kg). These findings were noted to be reversible and mild in severity In a 14-day repeat dose Safety Respiratory Study in monkeys, no respiratory effects on total pulmonary ventilation (minute volume) or respiratory rate were observed at doses of 1 or 10 mg/kg/day. See IB for GSK2982772 [GlaxoSmithKline Document Number 2014N204126_02].
	
Subject Monitoring:
 
 
Subjects should be monitored for standard respiratory-related adverse events.
 
Vital signs will be monitored during study visits.
 

Potential Risk of Clinical Significance	Summary of Data/Rationale for Risk	Mitigation Strategy
	
Clinical data: In the FTiH study, repeat doses of GSK2982772 were administered x 14 days in 36 healthy male volunteers. Extensive respiratory monitoring with end-tidal CO2 (ETCO2), oxygen saturation (SpO2) and nocturnal respiratory rate monitoring was performed. No SAEs occurred, and no drug-associated respiratory-related adverse events were identified.
	
Suicidality	
GSK2982772 is considered to be a CNS-active drug based upon pre-clinical studies.
 
Clinical data: In the FTiH study, there have been some reports of lethargy, abnormal dreams, and depressed mood. No events of suicidal ideation or behaviour or changes in behaviour were reported.
	
Subject Selection:
 
 
Subjects with a current history of suicidal ideation and behaviour (SIB) as measured using the Columbia Suicide Severity Rating Scale (C-SSRS) or a history of attempted suicide will be excluded from the study.
 
 
Subject Monitoring:
 
 
Subjects should be monitored appropriately and observed closely for suicidal ideation and behaviour or any other unusual changes in behaviour.
 
Baseline and treatment emergent assessment of suicidality will be conducted by trained site personnel using the (Columbia Suicide Severity Rating Scale) C-SSRS in all subjects. See Section 7.3.7.
 

Reproductive toxicity	
Non-clinical data: In an early rat embryofetal development study, there was no maternal or developmental toxicity at doses <math>\leq</math>200 mg/kg/day. In a rabbit embryofetal development study, GSK2982772 was administered at doses of 0, 10, 100, 300 or 600 mg/kg/day on gestation day 7 to 19. No developmental toxicity was evident at doses up to 300 mg/kg/day.
	
Subject Selection:
 
 
Male and female subjects of childbearing potential will be included in this study only if they agree to use highly effective methods of contraception and avoid conception for defined periods of time before first administration of study drug until 30days (females) and 90 days (males) after the last administration of study drug (Appendix 6).
 
Females of childbearing potential will undergo serum pregnancy test at screening and then urine pregnancy testing at regular intervals during the study.
 
Pregnant and lactating females are not eligible for
 

Potential Risk of Clinical Significance	Summary of Data/Rationale for Risk	Mitigation Strategy
		
inclusion in the study.
 
Withdrawal Criteria:
 
 
If a female subject should become pregnant during the study, study medication should be discontinued. The subject will be followed to determine the outcome of the pregnancy. Any pregnancy complication or elective termination of a pregnancy will be reported as an AE or SAE.
 

Drug Interaction	
Non-clinical data:
 
In vitro studies with GSK2982772 assessing potential drug-drug interactions with Cytochrome P450 3A4 (CYP3A4) substrates, P-glycoprotein (Pgp) inhibitors and OAT3 substrates were completed. To date, formal drug interaction studies in humans have not been performed with GSK2982772.
 
There is a low risk that GSK2982772 could be a perpetrator of OAT3 substrates. MTX is an OAT3 substrate in which GSK2982772 could potentially impair the clearance of MTX.
 
There is a low risk that GSK2982772 could be an inducer of CYP3A4 and therefore may lower circulating levels of concomitant medications that are metabolised by CYP3A4 when co administered with GSK2982772.
 
GSK2982772 is a Pgp substrate and therefore co administration with concomitant medications that are Pgp inhibitors could increase circulating levels of GSK2982772. See Section 4.3.6 of the GSK2982772 IB [GlaxoSmithKline Document 2014N204126_02].
	
Subject Selections:
 
 
Subjects who are taking concomitant medications known to inhibit Pgp or are CYP3A4 narrow therapeutic index (NTI) substrates will be excluded from the study. See Section 6.11.2 for a comprehensive list of medications.
 
 
Subject Monitoring:
 
 
Subjects' concomitant medication usage will be reviewed prior to inclusion and monitored throughout the study.
 
Subjects should be monitored throughout the study for potential effects of interaction between GSK2982772 and other concomitant medications.
 
PK sample collection to evaluate the potential interaction of GSK2982772 and MTX will be performed throughout the study.
 
Subjects should be monitored for potential effects of interaction between GSK2982772 and MTX.
 
Clinical laboratory results (e.g., liver function tests) are routinely being monitored throughout the study.
 

Potential Risk of Clinical Significance	Summary of Data/Rationale for Risk	Mitigation Strategy
Study Procedures		
Synovial Joint Biopsy	
Potential risks of the procedure include discomfort, infection or bleeding.
 
Note: Synovial biopsies are optional and not required on all subjects.
	
Subject Selection:
 
 
Subjects with known allergy to lidocaine or other local anaesthetics will not be included in the biopsy portion of the study.
 
Subjects with a platelet count <math>\leq 100 \times 10^9/L</math> will be excluded from participation.
 
 
Subject Management:
 
 
The biopsies will be performed under ultrasound or arthroscopic guidance. Subjects will be given instructions for aftercare and contact information should there be any adverse reactions after the procedure.
 
Biopsy site healing will be monitored during the study as part of AE safety review.
 

Gadolinium (Gd) containing MRI contrast agents	
Non-clinical data: Animal studies have shown reproductive toxicity of gadolinium (Gd)-containing MRI contrast agents at repeated high doses.
 
Clinical data: Use of MRI contrast agents in subjects with severely impaired renal function (GFR<30mL/minute) has been associated with Nephrogenic Systemic Fibrosis (NSF). In subjects with severely impaired renal function, the benefits of the use of contrast agents should be carefully weighed against the risks.
 
Gadolinium (Gd) contrast agents can be associated with anaphylactoid/hypersensitivity or other idiosyncratic reactions, characterized by cardiovascular, respiratory, or
	
Subject Selection:
 
 
Pregnant or lactating females will be excluded from taking part in the study.
 
Subjects with impaired renal function (GFR<60mL/minute) are excluded by the eligibility criteria.
 
Subjects with history of sensitivity to Gd-containing contrast agents will be excluded from the study. The MRI procedure will be conducted under the supervision of trained and qualified clinical staff that is trained to appropriately manage an allergic reaction.
 
Sites will be responsible for following any additional safety information for the specific Gd contrast agent used at their site and not enroll subjects if contraindicated.
 

Potential Risk of Clinical Significance	Summary of Data/Rationale for Risk	Mitigation Strategy
	
cutaneous manifestations, and ranging to severe reactions including shock. In general, subjects with cardiovascular disease are more susceptible to serious or even fatal outcomes of severe hypersensitivity reactions. The risk of hypersensitivity reactions may be higher in cases of:
 
 
• Previous reaction to contrast media
 
• History of bronchial asthma
 
• History of allergic disorders
 
 
Most of these reactions occur within half an hour of administration. Delayed reactions (after hours or several days) have been rarely observed.
	
Subject Monitoring and Management:
 
 
• MRI contrast at a dose less than or equal to 0.1 mmol/kg per imaging session at baseline and Days 43 and 85 will be used in the MRI protocol.
 
• Effective contraception is required during the study, and pregnancy testing will be performed regularly throughout the study and prior to dosing in females of child bearing potential.
 

Other		
Exposure to a high field MRI magnet	Certain prostheses or foreign bodies might be incompatible with the MRI scanner.	
Subject Selection:
 
 
• All participants will be screened according to local hospital criteria and study inclusion/exclusion before entering the MRI scanner to ensure they are able to have the MRI conducted. Subjects with non-magnetic resonance compatible metal implants or implantable electronic devices (e.g., pacemaker, defibrillator) will not be included in this study.
 

#### 4.6.2. Benefit Assessment

There are additional treatment options available for subjects who have an inadequate response to current therapies for RA. It is possible that treatment with GSK2982772 may be effective in the treatment of RA, as the FTiH study demonstrated that the drug engaged with the target and produced *ex vivo* PD effects in suppression of RIP1-dependent cytokines MIP1 $\alpha$  and MIP1 $\beta$  [GlaxoSmithKline Document Number [2014N204126\\_02](#)]. There will be limited direct benefit to the subject through their contribution to the process of developing new therapies in an area of unmet need.

#### 4.6.3. Overall Benefit:Risk Conclusion

Taking into account the measures taken to minimize risk to subjects participating in this study, the potential risks identified in association with GSK2982772 are justified by the anticipated benefits that may be afforded to patients with RA by contributing to the understanding of the disease and the development of new therapies for patients with these conditions in the future.

### 5. SELECTION OF STUDY POPULATION AND WITHDRAWAL CRITERIA

Specific information regarding warnings, precautions, contraindications, adverse events, and other pertinent information on the GSK investigational product (IP) or other study treatment that may impact subject eligibility is provided in the IB [GlaxoSmithKline Document Number [2014N204126\\_02](#)].

In addition, Investigators are expected to follow local and/or national guidelines with respect to vaccinations, including vaccinations for influenza and pneumococcus, in subjects with RA.

Deviations from inclusion and exclusion criteria are not allowed because they can potentially jeopardize the scientific integrity of the study, regulatory acceptability or subject safety. Therefore, adherence to the criteria as specified in the protocol is essential.

#### 5.1. Inclusion Criteria

A subject will be eligible for inclusion in this study only if all of the following criteria apply:

AGE
1. Between 18 and 75 years of age inclusive, at the time of signing the informed consent.
TYPE OF SUBJECT AND DIAGNOSIS INCLUDING DISEASE SEVERITY
2. Subjects that do not have any medical conditions, other than moderate to severe RA that in the opinion of the Investigator put the subject at unacceptable risk or interfere with study assessments or integrity of the data. These medical conditions should be

stable at the time of screening and are expected to remain stable for the duration of the study.

3. Subject has had a confirmed diagnosis of rheumatoid arthritis according to the revised 2010 American College of Rheumatology/European League Against Rheumatism ACR-EULAR classification criteria.
4. Disease duration of  $\geq 12$  weeks (time from onset of patient-reported symptoms of either pain or stiffness or swelling in hands, feet or wrists) at screening.
5. Swollen joint count of  $\geq 4$  (28-joint count) and tender joint count  $\geq 4$  (28-joint count) at screening.
6. Subject has a DAS28 CRP disease activity score of  $\geq 3.2$  and CRP  $\geq 5.0$  mg/L ( $\geq 4.76$  nmol/L) at screening.
7. Subject must have received at least 12 weeks of non-biologic DMARD monotherapy or methotrexate (MTX)/DMARD combination therapy prior to screening AND must be on stable dose throughout the study.
8. Subject is naive to any biological therapies for RA

**OR**

Subject may have had previous exposure to a single anti-TNF biologic agent which was discontinued for reasons other than primary non-response more than 8 weeks (or 5 half lives whichever is longer) from first dose. **Note: Exposure to a single anti-TNF is not required in addition to Inclusion #7 above.**

9. For subjects who have consented to synovial joint biopsy:
  - a. Subject has an involved knee, wrist, or ankle suitable for biopsy, as assessed by a rheumatologist at screening.

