#### 7.3.6. Clinical Safety Laboratory Assessments

All protocol required laboratory assessments, as defined in Table 3, must be conducted in accordance with the Laboratory Manual, and Protocol Time and Events Table (Section 7.1). Laboratory requisition forms must be completed and samples must be clearly labelled with the subject number, protocol number, site/centre number, and visit date. Details for the preparation and shipment of samples will be provided by the laboratory and are detailed in the laboratory manual. Reference ranges for all safety parameters will be provided to the site by the laboratory responsible for the assessments.

If additional non-protocol specified laboratory assessments are performed at the institution's local laboratory and result in a change in subject management or are considered clinically significant by the Investigator (e.g., SAE or AE or dose modification) the results must be recorded in the CRF.

Refer to the laboratory manual for appropriate processing and handling of samples to avoid duplicate and/or additional blood draws.

All study-required laboratory assessments will be performed by a central laboratory, apart from:

- Haematology, platelets and coagulation sample if they are required to be taken closer to the biopsies (as per local practices) than specified in Section 5.4.5.

**NOTE:** Local laboratory results are only required in the event that the central laboratory results are not available in time for either a treatment and/or response evaluation to be performed. If a local sample is required, it is important that the sample for central analysis be obtained at the same time. Additionally, if the local laboratory results are used to make either a treatment or response evaluation, the results must be entered into the CRF.

Haematology, clinical chemistry, urinalysis and additional parameters to be tested are listed in [Table 3](#).

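### Inclusion criterion 6 gives the CRP entry threshold as 5.0 mg/L and, as its equivalent, 4.76 nmol/L; the two values disagree by a factor of about 8 to 10

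*Protocol*

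**What the plan says.** Protocol section 5.1, criterion 6, sets two screening conditions: a DAS28-CRP score of at least 3.2, "and CRP $\geq 5.0$ mg/L ( $\geq 4.76$ nmol/L) at screening". The same pair of CRP values stands unchanged in section 5.1 of the Amendment 4 text, the country-specific version for Germany. No other section gives a CRP threshold, a molar mass or a conversion factor that would explain the pair.

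Section 5 makes the criteria binding: "Deviations from inclusion and exclusion criteria are not allowed".

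On measurement, section 7.3.6 states: "All study-required laboratory assessments will be performed by a central laboratory, apart from" haematology, platelet and coagulation samples that local practice wants nearer to a biopsy. CRP is not in that exception. Table 3 lists it under clinical chemistry, and the Time and Events Table schedules it at screening. The protocol does not say in which unit the central laboratory reports CRP.

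**The concern.** A bracketed value after a threshold normally restates it in another unit. Exclusion criterion 23 uses this layout and its pairs match: 3,000/mm³ is 3.0 × 10⁹/L, and 100,000/µL is 100 × 10⁹/L. Nothing suggests that criterion 6 instead offers two alternative thresholds. If the molar figure is not the equivalent of the mass figure, the sentence contains two different entry rules.

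What is at stake is whether eligibility can be decided without ambiguity. For a subject whose CRP lies between the two values, the criterion is both met and not met, and a monitor could not say whether a deviation had occurred. CRP also enters DAS28-CRP and the ACR response and is a named secondary inflammatory marker, so the threshold bears on who contributes to those endpoints.

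**Working it through.** **Inputs from the protocol (section 5.1, criterion 6)**

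- Mass threshold: 5.0 mg/L = 5.0 × 10⁻³ g/L
- Molar threshold: 4.76 nmol/L = 4.76 × 10⁻⁹ mol/L

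**Assumed input (not in the protocol)**

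- Molar mass M of circulating CRP (the pentamer): 105,000 to 125,000 g/mol. As a variant, the single subunit: 23,000 to 25,000 g/mol.

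**Step 1. Molar mass implied by the stated pair**

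M = (5.0 × 10⁻³) / (4.76 × 10⁻⁹) = 1.05 × 10⁶ g/mol, or about 1,050 kDa. Only at this mass does the bracket restate the mass threshold, and it is roughly ten times the assumed pentamer mass.

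**Step 2. Convert 5.0 mg/L to nmol/L, and 4.76 nmol/L to mg/L**

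nmol/L = (5.0 × 10⁻³ / M) × 10⁹ and mg/L = 4.76 × 10⁻⁹ × M × 10³

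| Assumed M (g/mol) | 5.0 mg/L in nmol/L | Ratio to 4.76 | 4.76 nmol/L in mg/L |
|---|---|---|---|
| 105,000 | 47.6 | 10.0 | 0.50 |
| 115,000 | 43.5 | 9.1 | 0.55 |
| 120,000 | 41.7 | 8.8 | 0.57 |
| 125,000 | 40.0 | 8.4 | 0.60 |

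The stated 4.76 nmol/L is not reproduced anywhere in this range.

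**Step 3. Does the subunit mass rescue the figure?**

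At 23,000 to 25,000 g/mol, 5.0 mg/L is 217 to 200 nmol/L, a 46- to 42-fold gap. The mismatch widens.

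**Step 4. Where the two limbs disagree**

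- CRP of 5.0 mg/L or more meets both limbs.
- CRP below about 0.5 to 0.6 mg/L (10% to 12% of 5.0 mg/L) meets neither.
- Between these, the subject fails the mg/L limb and passes the nmol/L limb. For example, 2 mg/L is 2 × 10⁻³ / 105,000 × 10⁹ = 19.0 nmol/L, or 16.0 nmol/L at 125,000 g/mol. It is below 5.0 mg/L but well above 4.76 nmol/L.

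**The case against.** The strongest reply concerns consequence. CRP is tested centrally, and nothing shows that any laboratory reports it in nmol/L. The note in section 7.3.6 that allows local results concerns treatment or response evaluation, does not mention eligibility, and requires a central sample at the same time. The mg/L figure comes first and the molar figure is only a gloss. This stands, and it makes the practical risk low. It does not remove the contradiction, because the protocol never names the reporting unit.

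A second reply is that the error can be called an error only with a molar mass from outside the document. That also stands as a limit. The conclusion nevertheless survives every mass tried, including the subunit.

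A reader might infer more than the documents support:

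- **That sites would enrol subjects with about one tenth of the intended CRP.** That fraction is the lowest value the molar limb admits, not a typical one. It also presumes that the mg/L figure is the intended one and that results are read in molar units.
- **That CRP-based endpoints would be diluted.** Criterion 5 (at least 4 swollen and 4 tender joints) and the DAS28-CRP minimum of 3.2 still require active disease. CRP is one of four DAS28 components and one of five remaining ACR measures, of which three must improve. The primary objective is safety, and section 9.2.1 says that the study is not powered for pre-defined differences. Nothing in the protocol allows the number of affected subjects, or any dilution, to be estimated.
- **That 4.76 is 47.6 with a misplaced decimal.** The digits match at 105,000 g/mol but not at 115,000 or 125,000 g/mol, so this is a conjecture about cause.

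**Conclusion.** Criterion 6 is wrong as written. Its two CRP values are not equivalent: they imply a molar mass of about 1,050 kDa, and at an assumed 105 to 125 kDa they differ by a factor of 10.0 to 8.4. The result is a band of CRP, from about 0.5 or 0.6 mg/L up to 5.0 mg/L, in which one binding criterion gives two opposite answers on eligibility.

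Severity is minor. The problem bites only if CRP is read in nmol/L, and central testing makes that less likely. The size of the gap rests on the assumed molar mass; the existence of a gap does not depend on the exact value chosen within any range tried. The documents do not establish that any subject would be admitted wrongly or that any endpoint would be affected, and they do not show which of the two figures is the intended one.

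**What to change.** Have the sponsor confirm the intended CRP threshold and the unit in which the central laboratory reports CRP. Then do one of the following, identically in section 5.1 of the Amendment 3 and Amendment 4 texts:

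- delete the bracketed molar figure as redundant, which needs no molar mass; or
- keep both units and make them agree, using the central laboratory's own conversion.

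A molar value computed from the masses assumed here should not be written into the criterion, because that would put an outside assumption and a choice of threshold into an eligibility rule.

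The cost is one figure in each text at the next amendment, with no operational cost.
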